from linear regression to mixed-effect models to complicated mediation analyses, all using the same state-of-the-art optimization and data handling methods. For example, prelinguistic communication skills are measured both: (a) continuously during intervention (via a language sample) and (b) after intervention (via the CSBS). As such, analysis of the effects of intervention on prelinguistic skills features two similar analyses: a latent growth curve of the monthly language sample (analysis 1.2a) and a linear regression for CSBS scores (analysis 1.2b). These two analyses answer similar questions (e.g., what is the direct effect of intervention on child prelinguistic skills) that differ based on the data on which they depend. Analysis 1.2a predicts month-to-month growth in child prelinguistic communicative acts, while 1.2b predicts a single CSBS score. These two modeling frameworks vary in their complexity and their modeling assumptions, specifically that latent growth curves estimated via SEM have more robust missing data handling than conventional regression software that requires complete cases. Estimating all models as SEMs means that all models retain the same underlying full sample sizes and assumptions, so that disparate results can be more directly attributed to constructs. In this example, stronger effects on monthly prelinguistic skills would reflect more proximal effects of intervention rather than a weakness of conventional regression methods and their missing data assumptions.

Data reduction of primary outcomes. Our multi-method approach requires data reduction and integration within and across time points. We will create a set of continuous latent indicators of child prelinguistic communication, child spoken language outcomes and parent use of communication support strategies. We will create these latent indicators using confirmatory item factor analyses, which allow us to combine the categorical data handling of an item response model with the flexibility to incorporate multidimensionality and specific measurement hypotheses common to factor analyses. We will further use multi-trait, multi-method approaches and related bifactor models when constructs span multiple modes of assessment (observational, elicited, parent report). See Table 1 for a summary of primary outcome constructs.

Table 1. Primary outcome constructs by analysis					
Construct	Measurement Structure	Measures	Variables Extracted	Measurement Occasions	Variable Type by Analyses

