Parent Use of Communication Support Strategies	Latent	Parent use of communication support strategies coded from a parent-child interaction	The following measures from the coded parent-child interaction sample: Percentage of intervals in which the adult is	Monthly from 12 to 18 months of age (6 time points between pre and post)	Analysis 1.1: Dependent Analysis 2.1: Dependent Analysis 4.1a: Mediator Analysis 4.1b: Mediator
			communicating within the child's line of sight Percentage of adult communication that is paired with a gesture in the child's line of sight Percentage of intervals in which the adult's play is related and is in close proximity to the child Percentage of child nonverbal actions that are mirrored and mapped Percentage of child communication that is followed by a contingent response Percentage of adult communication that is in response to child communication Percentage of adult communication Percentage of adult communication that contains a child linguistic target Percentage of child communication to which the adult imitates and adds a word	Monthly from 18 to 36 months of age (18 time points between post and follow-up)	Analysis 3.1: Dependent Analysis 4.2a: Mediator Analysis 4.2b: Mediator
Child Prelinguistic Communicative Acts	Latent	Language Sample	Number of child prelinguistic communicative acts coded from the language sample	12 to 18 months of age (6 time points between pre and post)	 Analysis 1.2a: Dependent Analysis 2.2a: Dependent Analysis 2.3a: Dependent Analysis 4.1a: Dependent Analysis 4.3a: Mediator
Child Overall Prelinguistic Skills	Observed	Communication and Symbolic Behavior Scale (CSBS)	Total Scaled Score	At 18 months of age (post)	 Analysis 1.2b: Dependent Analysis 2.2b: Dependent Analysis 2.3b: Dependent Analysis 4.1b: Dependent Analysis 4.3a: Mediator Analysis 4.3b: Mediator
Child spoken words	Latent	MacArthur-Bates Communicative Development Inventory; Language Sample	Total number of Words Said from the MacArthur- Bates Communicative Development Inventory Total number of different spoken word roots from the language sample	18 to 36 months of age (18 time points between post and follow-up)	 Analysis 3.2a: Dependent Analysis 4.2a: Dependent Analysis 4.3a: Dependent
Child overall spoken language	Observed	Preschool Language Scale-5 th Edition	Total Standard Score	At 36 months of age (follow-up)	Analysis 3.2b: DependentAnalysis 4.2b: DependentAnalysis 4.3b: Dependent

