Power for tests of intervention effects were estimated using G*Power⁹⁵ supplemented with custom simulations to verify accuracy and tailor assumptions to our research design. Given a sample size of 86 (96 recruited participants with 10% attrition), we project greater than 99% power for main effects of the intervention (aim 1) as large as those shown in our pilot study (d=1.07) (see Justification and Feasibility in Research Strategy). We further project 80% power for effects as low as d=.61 and 90% for d=.71. Each of the three previous estimates assume control for pre-test and 10% attrition (e.g., n=86). Our research group has maintained greater than 95% retention in comparable studies over the last two years. We would retain power for smaller effect sizes of d=.58 (80% power, down from d=.61) and d=.67 (90% power, down from d=.71) if no attrition occurs.

The above power analysis covers the primary analyses for Aims 1 and 3. However, these aims also include growth in parent and child outcomes assessed monthly. These analyses depend on latent growth curve models, as described above and require a simulation-based power estimate, as described in Zhang & Wang (2009). We simulated our monthly assessments four thousand times, varying our predicted effect size and distribution of latent intercepts and slopes. This simulation yielded reliable power estimates for each effect size. The use of longitudinal data yield improved power over our simple pre-test-post-test designs in the previous paragraph. We project 80% power for d=.34, and 90% for d=.45. Furthermore, we have 80% power to detect moderators (aim 2) that account for 7.8% of variance in the outcome or greater, and 90% for 10.4% of variance. In summary, this study is well-powered to test the effects of intervention on parent and child outcomes.

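### The growth-curve power pair (80% at d=.34, 90% at d=.45) cannot describe one fixed scenario, and the SAP does not say which scenario or scenarios it covers

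*SAP*

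**What the plan says.** The SAP's Power Analysis section has two parts.

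- **Pre-post comparisons.** With 86 participants: "We further project 80% power for effects as low as d=.61 and 90% for d=.71". With all 96: "We would retain power for smaller effect sizes of d=.58 (80% power, down from d=.61) and d=.67 (90% power, down from d=.71". The SAP says this calculation covers the primary analyses of Aims 1 and 3. Protocol section 4.0 repeats these figures.
- **Monthly growth outcomes.** These rest on a simulation of four thousand runs, carried out by "varying our predicted effect size and distribution of latent intercepts and slopes". The result is "We project 80% power for d=.34, and 90% for d=.45". This pair appears only in the SAP. No sample size, alpha, visit schedule, latent variances or definition of d is attached to it.

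The section ends with a moderator pair for Aim 2, for effects that "account for 7.8% of variance in the outcome or greater, and 90% for 10.4% of variance".

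The growth outcomes fall in two windows. In the SAP table headed "Table 1. Primary outcome constructs by analysis", parent strategy use is listed as "Monthly from 12 to 18 months of age (6 time points between pre and post" for the first window and "Monthly from 18 to 36 months of age (18 time points between post and follow-up" for the second. The power pair is assigned to neither.

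**The concern.** Two points on the same power curve are tied together: once the effect giving 80% power is fixed, so is the effect giving 90%. The growth figures lie too far apart for one curve.

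This sentence is the only power statement for the main-effect growth analyses 1.1, 1.2a, 3.1 and 3.2a. For parent strategy use and spoken-word growth, the growth model is the only main-effect test of the construct. As written, a reader cannot tell what power the trial has for a growth effect of .34, nor under what conditions.

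**Working it through.** **Inputs.** The d values and the sample sizes 86 and 96 come from the SAP's Power Analysis. Alpha and allocation are not stated there; I assume two-sided 5% and 1:1. Allocation cancels in the ratio used below.

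**1. Reproduce the plan's own pre-post figures.** A two-sample t-test at two-sided 5% gives:

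- 43 per arm: d = .611 for 80% and .707 for 90% (stated .61 and .71).
- 48 per arm: d = .578 for 80% and .669 for 90% (stated .58 and .67).

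Both pairs reproduce, which supports the alpha assumption.

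**2. Ratio expected on one curve.** With a fixed standard error SE, power(d) = Φ(d/SE − 1.960). So

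d90/d80 = (1.960 + 1.282)/(1.960 + 0.842) = 3.242/2.802 = 1.157.

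Sample size, number of visits, variances and reliability enter only through SE and cancel.

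**3. Ratios stated.**

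- Pre-post, n=86: .71/.61 = 1.164.
- Pre-post, n=96: .67/.58 = 1.155.
- Growth: .45/.34 = 1.324. Rounding of d allows .445/.345 = 1.290 to .455/.335 = 1.358.

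**4. Size of the discrepancy under one scenario.**

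- Take 90% at .45 as right: power at .34 = Φ(3.242 × .34/.45 − 1.960) = 68.8% (67–71% over rounding), and 80% power needs d = .45/1.157 = .389.
- Take 80% at .34 as right: power at .45 = Φ(2.802 × .45/.34 − 1.960) = 96.0% (95–97% over rounding), and 90% power needs only d = .34 × 1.157 = .393.

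A simulated linear growth model with fixed parameters (7 or 19 visits, 43 or 48 per arm) agreed: 79–81% power at the 80% point, and 95.6–96.6% at 1.324 times that effect.

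**5. Other explanations tried.**

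- *Another alpha.* The ratio is 1.177 at one-sided 5% and 1.207 at two-sided 20%; a stricter alpha lowers it. A ratio of 1.324 needs a two-sided alpha of about 0.60 (0.50–0.70 over rounding).
- *Mixed sidedness.* One-sided 5% for the 80% figure with two-sided 5% for the 90% figure gives 3.242/(1.645 + 0.842) = 1.304, which is inside the rounding range. Nothing in the SAP suggests this.
- *Mixed sample sizes.* 80% at 96 and 90% at 86 gives 1.157 × √(96/86) = 1.222, which is not enough.
- *Simulation noise.* At 4,000 runs per effect size the standard error is √(.8 × .2/4000) = 0.6 points and √(.9 × .1/4000) = 0.5 points, against gaps of 6 or 11 points. Runs per effect size are not stated. Cells of about 100 runs (standard errors 4 and 3 points) could produce the pair, but that sits badly with the SAP's description of the estimates as reliable.
- *Two separate scenarios or windows.* The standard error behind .45 would be (.45/3.242)/(.34/2.802) = 1.144 times that behind .34. In the less precise scenario, power at .34 is again about 69%.
- *Averaging over scenarios.* An equal mix of two scenarios set to 80% at .34 gives at least 91.7% at .45 (90.7% with favourable rounding). In a grid search, unequal mixes reproduce the pair only if the standard errors differ about 2-fold or more (1.9 with rounding of d). The weaker scenario then has at most about 52% power at .34 (56% with rounding).

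**6. The moderator pair is not a clean benchmark.** The stated ratio is 10.4/7.8 = 1.333 (1.318 at most favourable rounding). A noncentral F calculation (one tested term, three predictors, 5% alpha, all assumed) expects about 1.30 on the R-squared scale. On the f-squared scale the stated ratio is (.104/.896)/(.078/.922) = 1.372 against 1.339 expected. The fit is approximate either way, so the comparison here rests on the two pre-post pairs only.

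**The case against.** The strongest reply is that one fixed scenario is not the SAP's premise. The simulation deliberately varied the latent intercept and slope distributions, and averaging over scenarios of different precision flattens a power curve. A lognormal spread of standard errors with log-SD of about .49 gives exactly 80% and 90%. This stands: the pair is not impossible under every reading, and a reader who infers that a stated number has been shown to be wrong goes further than the documents allow.

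It does not make the sentence usable. Nothing in the SAP says that power was averaged or that the figures come from different scenarios. If either is so, the unqualified 80% at .34 fails in the less favourable scenario.

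A reader might also infer that power at .34 is overstated, or that the trial is underpowered. The documents support neither. If the .34 figure is right, the other is merely conservative. Even on the worse single-scenario branch, 80% power needs about .39, well below the pre-post .61, so the SAP's claim that monthly data improve power survives on its own d scale. The figure of about half power applies only if the pair is an average, which is not stated.

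Finally, the SAP treats the pre-post calculation as the one covering the primary analyses. That limits the consequence, although the growth outcomes do appear in its table of primary outcome constructs.

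**Conclusion.** The point holds in this form: the two growth figures cannot both belong to one scenario at two-sided 5%, since their ratio is 1.32 (at least 1.29) against 1.16. The SAP gives no scenario, or set of scenarios, under which they would. The ratio does not depend on sample size, visits or variances. It does depend on the assumed alpha, but no conventional alpha applied to both figures closes the gap.

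Under one scenario, the uncertainty is between about 69% and the stated 80% at .34, or between the stated 90% and about 96% at .45. The documents cannot settle which figure is off, whether both are, or whether the pair combines scenarios or the two windows.

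**What to change.** Recheck or re-run the existing simulation. Replace the sentence with an 80%/90% pair that belongs to one stated scenario, giving the sample size (86 or 96), analysis window, alpha and definition of d. If several scenarios or both windows were used, say so and report power for each, including the least favourable; stating the latent variances and the number of runs per effect size would let a reader check it. The cost is a check of existing code and one corrected passage in the SAP. Nothing changes in sample size, pre-post power, endpoints or models.

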The sample consists of 96 children with bilateral hearing loss and one of their caregivers (mother, father, grandparent). Children of all races and genders will be included in the sample. All children will be between 12 and 18 months of age) at the start of the study. Children will have a diagnosis of bilateral hearing loss. This age was chosen for several reasons. First, this is the age at which intentional communication usually emerges and prelinguistic communication skills develop. As such, this age is necessary to study the effects of early intervention on prelinguistic skills for young children with hearing loss. Second, children are typically seen for an audiology visit during this time, so it is an easy time to enroll study participants. Third, the majority of children are wearing hearing aids at this time. Fourth, 12 months is an age when we are able to test developmental processes that may influence response to intervention. Fifth, parents may be more likely to participate in research when their baby is older and after they have had time to process the diagnosis. Children will start the study around 12-18 months of age and continue in the study for 24 months.

Given a sample size of 86 (96 recruited participants with 10% attrition), we project greater than 99% power for main effects of the intervention (Aim 1) as large as those shown in our pilot study (d=1.07) (see Justification and Feasibility in Research Strategy). We further project 80% power for effects as low as d=.61 and 90% for d=.71. Each of the three previous estimates assume control for pre-test and 10% attrition (e.g., n=86). Our research group has maintained greater than 95% retention in comparable studies over the last two years. We would retain power for smaller effect sizes of d=.58 (80% power, down from d=.61) and d=.67 (90% power, down from d=.71) if no attrition occurs.

5.0 Research Locations:

All study procedures will occur in the homes of participants or at the Early Intervention Research Group at Northwestern University under the supervision of the principal investigator ([name]). Video conferencing services (such a zoom) will be used for all sessions, with the exception of "baseline only" activities and "eye tracking" activities.

Page 3 of 20 Revised: May 25, 2018

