All study activities will take place virtually, via a video call, with the exception of the eye tracking tasks, which will take place in the EIRG lab. After consent (explained below), all participants will complete the following pre-test child assessments, outlined in the table below. Given the nature of home testing the numbers of visits may vary based on timepoint and family. **Baseline only for children without hearing loss**: Children within the same age range who are typically developing without hearing loss will be invited to participate in pre (T0) testing only. Testing will remain in person (if allowed) for baseline only children.

Following pre-test, the naïve assessor and parent will complete monthly assessment visits with each child and parent in their home via video call for the entirety of the study (T1 - T24). During these visits, the assessor will collect a 12-minute language sample and a 12-minute parent child interaction. Parents will also complete parent surveys, which will be sent via email and include a REDCap link.

In addition to the monthly assessment sessions, the naïve assessor will also complete additional assessments with parent assistance at T0 (baseline, T7 (post-test) and T24 assessment (follow-up) via video call.

The parent and child will also participate in recorded video sessions with their speech therapist (SLP) two times throughout the study. For parents in Illinois, they parent and child will also be asked to participate in a video session with the child's developmental hearing therapist (DTH). This will not be done with parents in other states, since DTH services can vary by state. The parent videotape a typical early intervention session that takes place in the home. The video recorded sessions will be

Page 5 of 20 Revised: May 25, 2018

stored with all other research data, on password protected servers and drive. This component of the study allows researchers to see what other services parents and children are receiving in the community. After each early intervention therapy visit, the parent will also complete several surveys about the visit and the therapist.

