Monthly Doront	family members living in the home). The MacArthur-Bates Communicative Development Inventories (MCDI): Words and Gestures or Words and Sentences (the parent selects which words their child says and understands out of 680 words). English, Spanish, and American Sign Language versions (if applicable) Use of Community-Based Intervention	Parent	60 min.	Home	Monthly
Monthly Parent Surveys/Interviews	Services and Hearing Device Log (the parent answers questions about how many and what types of other therapy services their child received in the last month; indicates how often the child wears their hearing device across 8 different routines, such as meal times) Child's Communication – Survey about				
Visual Reception scale of the Mullen Scales of Early	child's communication The child is presented with different nonverbal tasks such as looking for a ring under a washcloth until the child fails to complete	Child	20 min.	Home or Lab	Post (T24)
Learning (MSEL) Goldman-Fristoe Test of Articulation – 3 rd edition (GFTA-3)	three consecutive tasks correctly. The GFTA-3 will take 20 minutes to administer. The GFTA-3 measures phonological skills by assessing an individual's articulation of the consonant and consonant cluster sounds of Standard American English. It provides information about an individual's speech sound ability by sampling both spontaneous and imitative sound production in single words and connected speech. GFTA-3 provides age-based normative scores separately for females and males for the Sounds-in-Words and Sounds-in-Sentences tests. Intelligibility is reported as a percentage score, and Stimulability information is reported in table format.	Child	20 min.	Home or Lab	Follow-up (T24)
Attention to Speech vs Sine-Wave Eye- Tracking Task	Children will be presented with two types of trials: speech sounds, and sinewave-transformed complex sounds. Once the child is attending to the screen, a trial will begin. Children will see either a red and white checkerboard pattern or a red and white bullseye. On speech trials, children will hear a random sequence of syllables ("lif" and "neem"). On sinewave trials,	Child (Chicagolan d participants only)	5 min.	Lab (if allowed by the state)	Pre (T0)

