Social Engagement Eye-Tracking Task	The child participates in two consecutive engagement conditions with animal hand puppets as the stimuli: (a) joint attention, (b) unavailable. Each condition includes six trials (six different puppets coming out of an opening). In the joint attention condition, the caregivers will respond only after the child vocalizes or gestures by looking back and forth between the puppet and the child and talking about the puppet. In the unavailable condition, the caregiver will read a book silently and will ignore all child communicative behavior.	Child (Chicagolan d participants only)	5 min.	Lab (if allowed by the state)	Pre (T0)
Communicative Insightfulness Assessment	The parent watches video clips of their child and determines when and why their child is communicating.	Parent (Chicagolan d participants	30 min.	Lab (if allowed by the state)	Pre (T0)

Revised: May 25, 2018

		only)			
Word Learning Eye-Tracking Task	Children will be presented with 29 trials total. On the first two trials, children will be familiarized to the task by seeing two familiar objects on the screen and asked to find one of them. Children will then be presented with images of two novel objects in order to familiarize them with the objects. Following this, children will see 2 movies, each 24 seconds long, that teach the child the name for reach of those new objects ("blick" and "modi"). After this, children are presented with four blocks of test trials. In each test block, children are given 4 test trials in which they are asked to find one of the new objects, and two reminder trials, where the new objects are shown and named in isolation.	Child (Chicagolan d participants only)	6 min	Lab (if allowed by the state)	Follow-up (T24)
Audiology Record Requests	Audiology records will be obtained to confirm degree of hearing loss. The parent will be asked to sign a specific hospital release form, so that we can request the child's audiology records.	Parent	NA	NA	Pre (T0) Post (T7) Follow-up (T24)
	SLP/DTH M		T < 0	1	T =
Early Intervention Therapist Observation (SLP, DTH)	The parent and child will participate in their typical therapy session with their SLP or DTH in their home and the session will be video recorded.	Parent/Careg iver and Child and SLP or DTH	60 min.	Home	Beginning of study (~T4) End of study (~30 months old)

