Data obtained from participants will include standardized, observational, and parent-report measures. All standardized and observational measures will be conducted by independent observers and assessors naïve to the experimental condition. Pre-test assessments will be administered in the participant's home via video call, with the exception of eye tracking measures for local participants. All additional time points will be conducted in the family's home. All standardized assessments and observational measures will be video recorded and coded. Parent report surveys will be collected using REDCap online surveys. Parents will be sent a unique link that gives them access to their unique list of surveys to be completed for that study time point. All surveys and assessments should be completed within a 10-day window to ensure data accuracy at each timepoint. Personal identifiable information (PII) (name, address, phone number, email address) will be collected on all parent/child dyads for the purposes of scheduling assessment visits, for conducting home intervention sessions, and for collecting survey data. Images of the face will be collected by video for the purpose of transcribing and coding parent-child interactions. Date of birth will be collected to determine child age at each time point so that we may include age in months in statistical analyses.

We propose a set of statistical analyses that firmly integrate our hypotheses and research design into a structural equation modeling framework to create a cohesive analytic plan that spans all study aims. Our aims further bridge the divide between

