9.0 Incomplete Disclosure or Deception: NA

10.0 Recruitment Methods:

Children will be recruited through Lurie Children's Hospital, pediatricians, Early Intervention providers, conferences, and online advertising. Participants are recruited in the Chicagoland area and nationally in the U.S. Clinicians who work with families of young children with hearing loss will be given a flyer to give to potentially eligible families. Clinicians may also direct them to our eligibility screener via the text-to-contact number on the flyer, where the caregiver will answer basic self-reported eligibility questions and give permission for EIRG study staff to contact them about their potential study participation. Study staff will then contact families that may be eligible for the study. Interested families may also contact EIRG directly via email, phone, or completing a recruitment survey on the EIRG website. **Baseline only for children without hearing**

Page 12 of 20 Revised: May 25, 2018

loss: Parents of children without hearing loss and with typical development will be invited to participate in baseline testing only.

11.0 Consent Process:

All consent forms will be approved by Northwestern University's Institutional Review Boards (IRB). All informed consent documents will contain the following: (a) an explanation of the purpose of the research, (b) expected duration of participation, (c) a description of research procedures, (d) foreseeable risks, discomforts, and benefits, (e) confidentiality and privacy of records and data, (f) contact information for who to contact to answer questions about the research process or participant rights and, and (g) a statement that participation is voluntary and that refusal will not result in penalty or change in their clinical services. Additional consent elements will also include financial information, alternative treatments, funding source, mandated reporter language, clinical trial information, and optional elements. All consent documents will contain layman's terminology when possible and use language appropriate to an 8th grade reading level. Consent documentation will include the date of IRB approval.

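### Aim 2 moderator power is stated without a sample size and fits the full cohort, but the protocol limits the eye-tracking moderators to Chicagoland families who attend the lab

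*SAP*

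**What the plan says.** The SAP's Power Analysis states that "we have 80% power to detect moderators (aim 2) that account for 7.8% of variance in the outcome or greater", with 90% power at 10.4%. The n of 86 in that section (96 recruited, less 10% attrition) is attached to the main-effect estimates, not to this sentence. The SAP overview adds that fitting everything by SEM keeps the full sample in every model.

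The Aim 2 moderators are all pre-test measures:

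- **2.1:** parental communicative insightfulness.
- **2.2a, 2.2b:** child sensitivity to social contingency, from a still-face procedure.
- **2.3a, 2.3b:** child attention to spoken language, from a looking-preference procedure.

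Protocol section 8.0, Table 1, restricts the speech-versus-sine-wave attention task to Chicagoland children, with location "Lab (if allowed by the state". The Social Engagement task and the Communicative Insightfulness Assessment ("The parent watches video clips of their child and determines when and why their child is communicating") have the same restriction. Section 10.0 says "Participants are recruited in the Chicagoland area and nationally in the U.S". Section 11.0 makes eye tracking an optional consent item for local families.

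On location, section 5.0 says "Video conferencing services (such a zoom) will be used for all sessions", excepting only baseline-only and eye-tracking activities. Section 8.0 says "All study activities will take place virtually, via a video call, with the exception of the eye tracking tasks", and later that pre-test assessments take place at "home via video call, with the exception of eye tracking measures for local participants".

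**The concern.** The power statement reads as if it applies to the whole trial, but at least one moderator is missing by design for every family outside Chicagoland and for local families who decline the lab visit. The 10% attrition allowance does not cover this, and neither document gives an expected or minimum number of children with moderator data.

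If a material share lack the moderator, a null interaction would be taken as coming from an 80%-powered test when it did not. The estimate would also describe local, lab-attending families rather than the randomised cohort. Aim 2 is one of the trial's specific aims and, unlike Aim 4, is not labelled exploratory.

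**Working it through.** **Inputs from the documents.** Power of 80% at 7.8% of variance and 90% at 10.4%; cohort of 96, or 86 after attrition (SAP, Power Analysis).

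**Assumptions, because the documents are silent.** Two-sided alpha of .05; a single interaction term tested in a regression; R²_other (variance explained by the remaining terms) from 0 to 40%; children with moderator data at 75%, 50% and 25% of 96, that is 72, 48 and 24. The alpha is supported by the SAP's main-effect figures, which reproduce at that level by noncentral t with no gain from pre-test adjustment: n=86 gives 79.8% at d=.61 and 90.2% at d=.71; n=96 gives 80.3% at d=.58 and 90.1% at d=.67.

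**Formula.** f² = R² / (1 − R²_other − R²), λ = n·f², noncentral F on 1 and n − k − 1 degrees of freedom. k = 3 when R²_other = 0 (treatment, moderator, product) and 4 otherwise (adding pre-test).

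**Reproducing the stated figures.**

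- R²_other = 0, R² = .078: f² = .078/.922 = .0846. At n=96, λ = 8.12 and power is 80.5%. At n=86, λ = 7.28 and power is 76.0%.
- R²_other = 0, R² = .104: f² = .104/.896 = .1161. Power is 91.0% at n=96 and 87.7% at n=86.
- R²_other = 9%, n=86: f² = .078/.832 = .0938, λ = 8.06, power 80.1%; at 10.4% of variance, 90.8%.

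The figures therefore fit 96 children with nothing else explained, or 86 with about 9% explained elsewhere.

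**What happens with fewer children measured.** Power for 7.8% of variance, with the variance detectable at 80% power in brackets:

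| Children with moderator | R²_other 0 | 9% | 25% | 40% |
|---|---|---|---|---|
| 72 | 68% (10.1%) | 73% (9.2%) | 81% (7.6%) | 90% (6.1%) |
| 48 | 50% (14.6%) | 55% (13.3%) | 64% (11.0%) | 75% (8.8%) |
| 24 | 27% (26.6%) | 30% (24.3%) | 35% (20.0%) | 44% (16.0%) |
| Needed for 80% at 7.8% | 95 | 86 | 70 | 55 |

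**Does FIML restore the full sample?** This was simulated with 96 children randomised 1:1, a normal moderator missing completely at random in 48, an interaction explaining 7.8%, one outcome, and 1,000 trials per setting. At R²_other = 0, the SD of the interaction estimate was 0.312 with FIML, 0.317 with complete cases and 0.202 with all 96 measured. Power was 50%, 46% and about 80% respectively. At R²_other = 25%, power was 62%, 57% and about 89%. The FIML test rejected 6.3% of the time under the null, so its power is slightly overstated. Children without the moderator stay in the model but tell it almost nothing about the interaction.

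**Which analyses are affected.**

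- **2.3a, 2.3b:** clearly. Table 1 restricts the speech-attention task to Chicagoland and the lab.
- **2.2a, 2.2b:** probably. The protocol lists no still-face procedure. The nearest task, Social Engagement, is restricted in the same way, but nothing says that it is the same measure.
- **2.1:** unclear. Table 1 restricts the insightfulness assessment to Chicagoland and the lab, whereas sections 5.0 and 8.0 exempt only eye tracking (and baseline-only activities) from video call.

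**The case against.** The strongest reply is that no shortfall has been shown. The local share, the opt-in rate and R²_other are all unknown, and some cells of the table meet 80%. This stands: the fault is an undisclosed assumption that the design makes doubtful, not a figure shown to be wrong.

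A second reply is that R²_other = 0 is unrealistically harsh. The plan adjusts for pre-test, and the pilot effect of d=1.07 alone would explain 1.07²/(1.07² + 4) = 22% of variance at 1:1 allocation. At 22%, 73 children suffice, power at n=72 is about 80%, and 11.4% is detectable at n=48. This also stands, so the zero column should be read as one end of a range. It does not rescue n=48, where power stays below 80% even at 40% explained.

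Third, the F test matches 2.2b and 2.3b directly but only approximates the latent-growth analyses 2.1, 2.2a and 2.3a. That is correct. It is nevertheless the natural reading of a threshold expressed as variance explained, and it reproduces both stated figures.

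Fourth, the SAP plans to add predictors of missingness as covariates, and these could recover information. They would do so only if they predicted the moderator strongly, and nothing in the documents suggests that they do.

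Finally, the mention of eye tracking in sections 5.0 and 8.0 may be shorthand for the whole lab visit. If so, the insightfulness measure is also local only, which widens the problem.

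**Conclusion.** The concern holds. The Aim 2 power statement has no stated basis, fits a full-cohort n, and is attached to moderators of which at least one is collected only in a local, opt-in subset. Its size depends on figures that the documents do not give. Keeping 80% power for 7.8% of variance takes between 95 children (nothing else explained) and 55 (40% explained). With half the cohort measured, power is 50% to 75%; with a quarter, 27% to 44%; with three quarters, 68% to 90%. These figures assume two-sided .05 and a one-term regression test, and are approximate for the growth-curve analyses. The point is firm for 2.3 and conditional for 2.2 and 2.1. It should be fixed, but it does not touch the Aim 1 and Aim 3 comparisons.

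**What to change.** - Restate Aim 2 power and detectable variance separately for 2.1, 2.2 and 2.3, at the number of children with observed moderator data. Give that n, the model and the assumed R²_other, and show a range where these are uncertain (for example, at n=48, 14.6% detectable with nothing else explained and 8.8% with 40% explained).
- Qualify the SAP overview's statement on full sample sizes: for Aim 2, FIML retains the children but adds little information on the interaction.
- State that 2.3, and 2.2 and 2.1 if their measures are lab-only, describe local lab-attending families, and that a null result there is not an 80%-powered null.
- Reconcile Table 1 with sections 5.0 and 8.0 of the protocol on where and in whom the Communicative Insightfulness Assessment is given.
- Reconcile the SAP's still-face procedure with the protocol's task list.

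The cost is wording in both documents and a less favourable stated power for Aim 2. Endpoints, estimators and data collection do not change.
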